## 7.6 Trial assessments

See Appendix 4.

## 7.7 Long term follow-up assessments

No long-term follow-up beyond the initial 6-month follow-up period is planned.

#### 7.8 Withdrawals

Patients are free to withdraw from the trial without reason at any time. Unless the participant specifically withdraws consent for their data to be stored, all data collected from them will continue to be stored as per the original patient consent. At a participant's request, their data collected up to the point of withdrawal can however be withdrawn from the trial and will not be used in the final analysis. Participants withdrawing from the trial will not be replaced. Patients may also withdraw from specific aspects of the trial data collection e.g., completion of questionnaires, but provide consent for collection of research data from their medical notes to be allowed to continue.

On participant withdrawal, data will be collected recording reasons for withdrawal (as far as possible). During the trial, the DMEC will review rates of withdrawals of different type, as well as the available reasons for these, and make recommendations regarding amendments to trial procedures, or retraining/discussion with trial investigators at any sites where these issues are most prevalent.

## 7.9 Departures from randomised treatment (non-adherence)

Clinicians/Investigators are free to deviate from a patient's assigned treatment allocation if clinically indicated. Where patients depart from their randomised treatment due to an error, efforts will be made to re-instigate their correct treatment allocation if possible, within 5 days of the change. Changes to the randomised treatment do not need to be reported to YTU as protocol deviations. Patients' data will continue to be collected regardless of any departures from the allocated treatment strategy to help

facilitate an intention-to-treat (ITT) analysis. During the trial, the DMEC will review data relating to adherence, and make recommendations regarding amendments to trial procedures as necessary.

## 7.10 End of trial

Relevant bodies including the trial sponsor and the Health Research Authority will be notified by YTU that the trial has ceased. The end of the trial is the date of the last patient last visit (LPLV). This is defined as: a. Completion of 6 month follow up assessments by the last randomised patient, or b. Withdrawal of the last randomised patient from planned follow up data collection

## 8 TRIAL STRATEGIES

This trial is comparing two antibiotic treatment duration strategies for the treatment of complicated intra-abdominal infection.

#### 8.1 Intervention

A fixed-extended-antibiotic duration of 28-days effective therapy for patients with cIAI. Effective antibiotic therapy is defined as therapy likely to be active against common pathogens causing cIAI and not limited by proven antimicrobial resistance detected pre-randomisation according to standard laboratory criteria.

## 8.2 Detailed specification of the intervention

The intervention is a strategy of a fixed-extended-duration antibiotic treatment of 28-days. The start of antibiotic therapy is the first day of effective therapy for cIAI treatment, which will generally occur before randomisation, but could be following randomisation if antibiotics given prior to randomisation are ineffective/inactive. The start date of antibiotic treatment will be determined by the patient's clinical team or clinical research team. Examples of antibiotic therapy that are not therapy for cIAI include antibiotic prophylaxis, or treatment for other infections e.g., cystitis. All treatment will be considered effective unless:

1) Antimicrobial resistance is identified on clinical samples collected before randomisation and that resistance is believed to be clinically relevant i.e., antibiotic treatment is changed based on the microbiological evidence of antibiotic resistance. The start date of fixed-extended-duration antibiotic treatment of 28-days will be re-set to day 0 where antibiotic treatment is changed based on pre-randomisation detection of antibiotic resistance. This strategy relates to the fixed-extended-duration treatment only, and the date of randomisation is not changed.

2) Antibiotics are prescribed for prophylaxis e.g., penicillin for splenectomy, elective surgery antibiotic prophylaxis, UTI prophylaxis

3) Antibiotics are prescribed for the treatment for other infections e.g., cystitis, and not effective against cIAI.

4) Antibiotics are oral antibiotics prescribed prior to hospitalisation

5) Antibiotics from a previous course of antibiotics, a previous course is one stopped for 48 hours or more.

The choice of antibiotic and route of administration are therefore selected by the treating clinician. Source control procedures (surgical and radiological) will be carried out as per standard practice.

#### 8.3 Comparator

Standard care antibiotic duration. We describe standard care as being based on clinician judgment. Clinicians use the clinical progress of the patient in combination with inflammatory blood markers, surgical and radiological findings to guide standard treatment antibiotic durations. Treatment durations are not pre-determined or fixed in duration. Standard care antibiotic durations do not dictate the choice or route of antibiotics; as per the intervention arm standard care refers to antibiotic durations only. Source control procedures (surgical and radiological) will be carried out as per standard practice. The start of antibiotic therapy is the first day of effective therapy. When antimicrobial resistance is identified and believed to be clinically relevant i.e., antibiotic treatment is changed based on microbiological results, the start of antibiotic therapy will be re-set to day 0 if this occurs within the first 10 days of treatment. The end date for standard antibiotic duration is defined by the first 48-hour period without antibiotic therapy. The end date is the first date within this 48-hour period.

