There are three published RCTs of antibiotic durations for cIAI; STOP-IT, DURAPOP and a cIAI feasibility trial [8, 12,13]. These trials all compared different antibiotic durations and together provide a signal of efficacy for longer antibiotic treatment durations. STOP-IT reported that a median of 4 days antibiotics was as effective as a median of 8 days, with surgical-site infection, recurrent intraabdominal infection, or death occurring in 21.8% as compared with 22.3% respectively (p=0.92). However, despite the limited difference in treatment durations, the longer antibiotic durations significantly delayed time until relapse (p=<0.001), which is consistent with an incompletely treated infection. DURAPOP assessed antibiotic durations for ICU patients with cIAI and compared 8 to 15 days of antibiotics. DURAPOPs secondary outcomes reported a significantly lower rate of radiological drainage in patients treated with 15 vs. 8 days antibiotics (9%, 11/116 vs. 19%, 23/120, p=0.04). Other outcomes signalled a 15-day treatment strategy may have benefits including: median length of ICU stay (12 days vs.13 day, p=0.14), rate of bacteraemia (4% vs.11%, p=0.059) and rate of microbiological failure (16% vs. 23%, p=0.13). The cIAI feasibility trial was a 30 patient RCT conducted in Leeds, UK, and designed after consultation with a Leeds Cancer-Patient and Public Involvement (LC-PPI) group [8]. It compared 28-days antibiotics to ≤10 days for patients with cIAI. It found a relapse rate of 4/17 (24%) in the ≤10-day arm, vs. 0/13 (0%) in the 28-day arm. Infections outside the abdominal cavity were diagnosed in 6/17 (35.3%) of those in the  $\leq 10$ -day arm, vs. 1/13(7.9%) in those treated for 28-days. Current UK practice and outcomes in patients with cIAI is described by a 417-patient observational study across 30 UK hospitals [5]. In the 17.3% of patients with relapse the median time until relapse was 18 days (IQR: 13-30 days); in the 11.3% of people who died the median time to death was 23 days (IQR: 12-51 days). Antibiotic treatment had a median duration of 12 days (IQR 7-18 days). The rate of adverse events in patients treated for cIAI varies by the patients group studied. Mortality rates have been reported at up to 50% in at risk populations with severe illness, and at 10 to 20% in studies from more broad populations of patients. The need for additional source control procedures, rate of relapses and rate of treatment failure likewise varies by population and definition, being reported in 20 to 60% of patients [2,3,15-19].

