## 4.1. Internal pilot

The EXTEND trial will incorporate a 12-month internal pilot phase which will assess setup and recruitment rates and monitor adherence with allocated antibiotic treatment durations. Site setup and recruitment will be assessed against the criteria given in the Table below (percentages indicate proportions recruited out of the end of pilot target). The thresholds in the "Green" column are based on reaching our recruitment target of 1166 in 36 months, assuming 30 sites are opened in a staggered manner over the first 24 months of the recruitment period. The thresholds in the "Red" column are based on the minimum values of these metrics for which (under certain assumptions) recruitment could still plausibly be completed in 36 months. Findings from the pilot phase will be used to remodel the projected recruitment trajectory for the main phase of the trial and, together with input from the trial oversight committees, inform any amendments necessary to achieve this trajectory. The trial team and oversight committees will also closely monitor the durations of antibiotics prescribed in each arm during the internal pilot phase. This will enable a proactive approach to managing and retraining sites where departures from the randomised allocations (as relates to antibiotic treatment durations) are identified and thereby ensure adequate separation of the two treatment groups. At the end of the internal pilot phase, the trial oversight committees and funder will review all elements of the pilot progression criteria, as well as data relating to adherence. They will advise whether the trial should; continue as planned or continue with minor or major amendments or enhanced monitoring/training, prior to making any recommendation on whether recruitment should be terminated early, if there is substantial evidence that the full trial is not feasible. Adherence to randomised allocation (standard and fixed-extended-duration antibiotic treatments) will be measured throughout the trial including in the internal pilot. Adherence rates will be reviewed at the end of the pilot phase.

	Red	Amber	Green
Recruitment rate (patients/site/month)	< 1.08	1.08 to 1.49	≥ 1.5
Number of sites opened	< 13 (< 65%)	13 to 20 (65% to 100%)	≥ 20 (≥ 100%)
Total number of participants recruited	< 144 (< 64%)	144 to 224 (64% to 100%)	≥ 225 (≥ 100%)
Separation (in days) between the average	< 5 days	5 to 10 days	> 10 days
antibiotic durations in treatment arms			

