#### 8.4 Assessment of adherence with treatment

Monitoring adherence to antibiotics prescribed while an in-patient will be carried out by monitoring patient's prescription charts. An amount of antibiotics prescribed orally may be consumed while an out-patient. We recognise the importance of adherence to ensure separation between the trial arms in terms of the intervention durations. We therefore need to review outpatient adherence within our internal pilot. We will do this by means of a modified Brief Adherence Rating Scale [25] in the 1-month participant questionnaire. There will be no process of formally assessing if antibiotic treatment is adherent to the protocol in those treated with standard care antibiotic treatment. In participants receiving a fixed extended-duration antibiotic treatment of 28 days, this will be considered protocol adherent where the overall treatment duration is within 5 days of this duration.

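### Section 8.3 starts the standard-care course on effective therapy but ends it on any antibiotic-free 48 hours, so prophylaxis or an unrelated course can lengthen the recorded duration

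*Protocol*

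**What the plan says.** Section 8.3 (Comparator) fixes both ends of the standard-care course. The start: "The start of antibiotic therapy is the first day of effective therapy". The end: "The end date for standard antibiotic duration is defined by the first 48-hour period without antibiotic therapy", with the end date being the first date in that period.

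Section 8.2 lists what does not count as effective treatment. Item 2 reads "Antibiotics are prescribed for prophylaxis e.g., penicillin for splenectomy, elective surgery antibiotic prophylaxis, UTI prophylaxis". Item 3 removes treatment of other infections, but only where the agent is not effective against cIAI. Section 6.1, footnote 2, has a similar list for the 10-day entry window. Neither list is attached to the end rule in 8.3. Section 8.2 also shows how the protocol uses the broader term: "Examples of antibiotic therapy that are not therapy for cIAI include antibiotic prophylaxis, or treatment for other infections e.g., cystitis".

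For the other arm, section 8.1 describes "A fixed-extended-antibiotic duration of 28-days effective therapy for patients with cIAI". No rule is given for when a recorded course in that arm ends. Section 8.4 calls a 28-day course adherent if its overall duration is within 5 days of 28, and says of the comparator: "There will be no process of formally assessing if antibiotic treatment is adherent to the protocol in those treated with standard care antibiotic treatment".

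The pilot table in section 4.1 includes the row "Separation (in days) between the average" antibiotic durations of the arms: red below 5 days, amber 5 to 10, green above 10. It names neither a start or end rule nor the type of average.

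**The concern.** The qualifier that limits the start of the course is missing from its end. Two foreseeable records show the effect of the literal wording:

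- A patient has 10 days of cIAI treatment and takes continuous penicillin after splenectomy, or continuous UTI prophylaxis. No antibiotic-free 48 hours occurs, so the course has no end date during follow-up.
- A patient has 9 days of cIAI treatment and starts 7 days of nitrofurantoin for cystitis the next day. Section 6.1 names nitrofurantoin as not effective for cIAI. The recorded duration is 9 + 7 = 16 days, not 9.

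The error can only lengthen the standard-care duration. If that duration is used for the pilot criterion, the arms look closer than they are, and the trial could be graded amber or red, or sites retrained, without cause. Even if a narrower meaning was intended, staff at 30 sites could code the same chart differently.

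**Working it through.** The protocol gives no computed figure for separation, only the colour thresholds, so there is nothing of its own to reproduce. The sample size does not depend on this point.

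**Inputs from the protocol.** Intervention duration 28 days (8.1). Current UK practice, section 1: "Antibiotic treatment had a median duration of 12 days (IQR 7-18 days"). Thresholds of 5 and 10 days (4.1). Follow-up 180 days. Infections outside the abdomen in 6/17 (35.3%) of the short-course arm of the feasibility trial (section 1).

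**Assumptions.** The intervention arm averages exactly 28 days. UK practice stands in for standard care. A share f of standard-care patients has the course extended by x days. Continuous prophylaxis is scored as 180 days, which is an upper value because many pilot patients will have shorter follow-up when the 12-month pilot ends. The protocol gives no prevalence for f.

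**Two models for the true standard-care mean m.**

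- Near-symmetric: m = 12, true separation 28 − 12 = 16 days.
- Skewed (lognormal): median 12, σ = ln(18/7)/1.349 = 0.70, which implies quartiles of 7.5 and 19.2. m = 12 × exp(0.70²/2) = 15.3, true separation 28 − 15.3 = 12.7 days.

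Both are green.

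**Continuous prophylaxis, mean used, rule applied to standard care only.** Recorded separation = (28 − m) − f(180 − m).

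| f | m = 12: 16 − 168f | m = 15.3: 12.7 − 164.7f |
|---|---|---|
| 2% | 12.6 (green) | 9.4 (amber) |
| 3% | 11.0 (green) | 7.8 (amber) |
| 5% | 7.6 (amber) | 4.5 (red) |
| 7% | 4.2 (red) | 1.2 (red) |

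Share at which green is lost: 6/168 = 3.6%, or 2.7/164.7 = 1.6%. Share at which red begins: 11/168 = 6.5%, or 7.7/164.7 = 4.7%. At the pilot target of 225 participants (about 112 per arm), 1.6% to 3.6% is about 2 to 4 patients.

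**Short contiguous courses, mean used, standard care only.** The loss is f × x.

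- f = 10%, x = 7: 0.7 day, leaving 15.3 or 12.0 (green).
- f = 35.3%, x = 7: 2.5 days, leaving 13.5 or 10.2 (green).
- f = 35.3%, x = 14: 4.9 days, leaving 11.1 (green) or 7.8 (amber).

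The 35.3% is an extreme illustration. It supposes that every such infection was treated without a 48-hour gap and with an agent not effective against cIAI.

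**Same literal rule in both arms.** Patients on prophylaxis score 180 in either arm, so separation = (1 − f)(28 − m). At f = 5% this is 0.95 × 12.7 = 12.1 days, still green. Reaching 10 days needs f = 1 − 10/12.7 = 21%.

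**Median instead of mean (skewed model).** Placing a share f at the top moves the standard-care median to the 0.5/(1 − f) quantile of the remaining distribution. For f = 1% to 5% the shift is about 0.1 to 0.6 day.

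**The case against.** The strongest reply is that the literal reading is not the only one. The end date closes the course that 8.3 has just opened with effective therapy. Section 6.1 also uses a 48-hour gap to separate treatment courses, with prophylaxis set aside in its own bullet. On that reading nobody would record lifelong penicillin as a 180-day cIAI course. This stands as far as showing that the text is ambiguous. It does not remove the defect, because 8.2 itself uses the broader term to cover prophylaxis and treatment of other infections.

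Several stronger readings are tempting, and the protocol does not support them:

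- **That the pilot criterion is distorted.** Section 4.1 does not cite the 8.3 end date or say mean or median. The link is an inference from 8.3 being the only stated end rule.
- **That the arms are measured differently.** Sections 8.1 and 8.2 define the 28-day strategy and its start. No measured end date is stated for that arm, so a difference is possible but not shown.
- **That the adherence-related sensitivity analyses are biased.** Section 10.2.3 announces alternative estimands without naming this duration, and 8.4 sets no formal adherence assessment in standard care.
- **That all treatment of other infections should drop out.** Item 3 of 8.2 removes it only when the agent is not effective against cIAI.

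The possible harm is also limited. Any error makes the pilot look worse, not better. Section 4.1 has no automatic stop: the committees review all criteria together, and early termination needs substantial evidence that the trial is not feasible.

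**Conclusion.** The rule in 8.3, followed as written, can give a wrong standard-care duration, and it should be corrected. The effect on the pilot is conditional. A change of colour at a few percent of patients requires the literal reading, a mean, application to one arm only, scoring to day 180, and a prevalence of long-term prophylaxis that the protocol does not supply. Given all of these, green is lost at about 1.6% to 3.6%, and red begins at about 4.7% to 6.5%, depending on how skewed durations are. With a median, or with one rule in both arms, the shift is below 1 day at up to 5%. Short follow-on courses change the colour only in the extreme case under the skewed model.

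The primary intention-to-treat analysis (10.2.3) does not use this date, nor does the secondary outcome of total days of antimicrobial therapy (10.2.4). No effect on the alternative estimands is shown.

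**What to change.** These changes concern measurement only and leave treatment as it is.

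1. In 8.3, define the end date as the first day of the first 48-hour period without effective antibiotic therapy for cIAI. Apply items 2 and 3 of 8.2 as they are worded, keeping item 3's condition that the agent is not effective against cIAI.
2. Apply the same measurement rule to recorded durations in both arms.
3. In 4.1, state that the separation criterion uses this duration, and whether the average is a mean or a median.

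The cost is a few sentences in the protocol and matching guidance for data entry. The one real burden is that indication must be judged for later courses as well as at the start. That is harder for outpatient courses, where section 3.6 relies partly on self-report.

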#### 8.4 Assessment of adherence with treatment

Monitoring adherence to antibiotics prescribed while an in-patient will be carried out by monitoring patient's prescription charts. An amount of antibiotics prescribed orally may be consumed while an out-patient. We recognise the importance of adherence to ensure separation between the trial arms in terms of the intervention durations. We therefore need to review outpatient adherence within our internal pilot. We will do this by means of a modified Brief Adherence Rating Scale [25] in the 1-month participant questionnaire. There will be no process of formally assessing if antibiotic treatment is adherent to the protocol in those treated with standard care antibiotic treatment. In participants receiving a fixed extended-duration antibiotic treatment of 28 days, this will be considered protocol adherent where the overall treatment duration is within 5 days of this duration.

## 9 PHARMACOVIGILANCE

# 9.1 Definitions

Term	Definition
Adverse Event	Any untoward medical occurrence in a participant to whom a medicinal product
(AF)	has been administered, including occurrences which are not necessarily
	caused by or related to that product.
	An untoward and unintended response in a participant to an investigational
	medicinal product which is related to any dose administered to that participant.
	The phrase "response to an investigational medicinal product" means that a
	causal relationship between a trial medication and an AE is at least a
Adverse	reasonable possibility, i.e., the relationship cannot be ruled out.
Reaction (AR)	All cases judged by either the reporting medically qualified professional or the
	Sponsor as having a reasonable suspected causal relationship to the trial
	medication qualify as ARs. It is important to note that this is entirely separate
	to the known side effects listed in the Summary of Product Characteristics
	(SmPC). It is specifically a temporal relationship between taking the drug, the
	half-life, and the time of the event or any valid alternative aetiology that would
	explain the event.
	Any untoward medical occurrence that:
	results in death
	
 
Is life-threatening*
 
requires inpatient hospitalisation or prolongation of existing hospitalisation
 

	
 
results in persistent or significant disability/incapacity
 

Serious	consists of a congenital anomaly or birth defect
Adverse Event	Other important medical events' may also be considered serious if they
(SAE)	jeopardise the participant or require an intervention to prevent one of the
(01-1-)	above consequences.
	*NOTE: The term "life-threatening" in the definition of "serious" refers to an
	event in which the participant was at risk of death at the time of the event; it
	does not refer to an event which hypothetically might have caused death if it
	were more severe.
Serious	An AE that is both serious and, in the opinion of the reporting Investigator,
Adverse	believed with reasonable probability to be due to one of the trial treatments,
Reaction (SAR)	based on the information provided.

A serious AR, the nature and severity of which is not consistent with the				
information about the medicinal product in question set out in the reference				
safety information:				

 
in the case of a product with a marketing authorisation, this could be in the
 
				
SmPC for that product, so long as it is being used within its licence. If it is being				
used off-label an assessment of the SmPC's suitability will need to be				
undertaken.				
• in the case of any other investigational medicinal product in the investigator's				
brochure (IB) relating to the trial in question				

